For frontal approach neurosurgical and neurointerventional procedures, the usual placement of the SedLine® sensor is challenging.

Numerous studies have already analyzed the accuracy of the change of position and the application of alternative positions for other devices used for depth of anesthesia monitoring (2,3,4,5). Albeit this, yet to date, there is no study that analyzed the application of alternative positions for the SedLine® sensors.

Research Questions and Hypotheses

The purpose of our study is to compare the standard Masimo SedLine EEG sensor frontal placement versus an experimental nasal placement of the SedLine® sensors for neuromonitoring. To determine whether this position generates similar data and validate this new alternate position.

We hypothesized that placing the central sensors in the montage approximately 2 cm below the standard recommended placement, across the nasal bridge and then running under the eyes to the normal temporal leads placement would put the entire montage out of the operative field and would still have corresponding values.

Study Design

Prospective cohort study.

Population

It is expected to recruit 40 patients undergoing general anesthesia. Considering a drop-out of 20%, we'll recruit 50 patients.

Duration of evaluation

Study participants will be evaluated only during surgery.

The study will be performed in an operation room during surgery, from the moment of induction to anesthesia up to a few minutes after the extubation. Setting up the sensor, time alignment in both Masimo Roots, as well as collecting and processing data from both sensors will be the standard approach for all 40 patients.

No further observation is needed.

Inclusion criteria

- Patients older than 18 years of age, both genders.
- Patients undergoing simple or complex surgery.
- American Society of Anesthesiologists Classification (ASA) score I to III.

Exclusion criteria

- American Society of Anesthesiologists Classification (ASA) score IV and V.
- Age below 18
- Previous neurological problems affecting EEG
- Dementia
- Use of sedative or drugs that can alter EEG readings
- Patients under head and neck surgery

PROCEDURES AND METHODS**Selection and recruitment of patients**

Patients are identified as potentially recruitable during the preoperative visit in the preoperative department. The anesthesiologist has to inform adequately patient. After this preliminary check for recruitment criteria, the patient will receive the informing module. The researcher confirms the recruitment criteria during the pre-surgical visit.

Data obtained during the study are confidential and during their presentation will not be discovered information that may reveal the identity of the patient.

Intervention

The authors will perform a prospective study, enrolling patients and performing neuromonitoring using both the standard (FRONTAL) and the alternative (NASAL) montage on each patient.

Evaluation

1. Primary end-point:

- We will monitor and compare processed electroencephalograph (EEG) values (PSi- Patient State Index, SEFL- Spectral Edge Frequency Left, SEFR- Spectral Edge Frequency Right, SR-Suppression Ratio, EMG-Electromyograph, ARTF-Artifact) and EEG waveforms, from nasal and frontal sensors.

2. Other data collected will include:

- Other parameters that will be measure are patient demographics (age, sex, surgery, ASA status, weight, height, BMI).

Plan of study

At least 40 patients are expected to be included after obtaining the approval of Ethical Committee. Patients will be included only if they sign informed consent for study.

The study includes a preoperative visit, perioperative observation.

STATISTICAL ANALYSIS

For each of the two modes of measurement, 1800 data points per subject (1 reading every 2 seconds for 1 hour) per hour will be collected. Assuming a maximum interclass correlation coefficient of .90, a sample size of 40 patients will be required to test the null hypotheses that the two modes of measurement share 95% of their variance via the construction of a 95% confidence interval that ranges no more than +-5%.

Analysis plan

The initial descriptive statistics will describe and summarize the patient characteristics.

Data from the 2 placements will be compared and analyzed using a Bland-Altman analysis and a matched-pair analysis.

Access to data and statistical processing of data will be available and compiled by the author of the study, [name] and CCAD biostatistician, [name].

Safety

Risks and Benefits

This prospective observational cohort study does not present greater than minimal risk for patient.

There is no prospect of direct benefit but we will gain knowledge that can help us in future neuromonitoring.

Data Safeguards

We will maintain data in a secure environment; we will use only CCAD laptop computers to store the data.

There will be two levels of password protection.

Safety Cont.

Consent

Patients are identified as potentially recruitable during the preoperative visit in the preoperative department. The anesthesiologist has to inform adequately patient. After this preliminary check for recruitment criteria, the patient will receive the informing module.

The researcher confirms the recruitment criteria during the pre-surgical visit.

Data obtained during the study are confidential and during their presentation will not be discovered information that may reveal the identity of the patient.

Adverse Events and Data Monitoring Committee (DMC)

Data Monitoring Committee is not planned but we will have regular meetings between principal investigators and co-investigators. This study does not present greater than minimal risk for patient.

Sponsorship

The use of SedLine® monitoring is a standard part of everyday anesthesia practice in our institute.

Additional resources (sensors) required for this study will be provided by the sponsor, Masimo Company. Masimo is a global medical technology company that develops and manufactures innovative noninvasive patient monitoring technologies, medical devices, and a wide array of sensors.

Masimo Company will provide 50 sensors that we need as addition to ours that we use as part of standard monitoring during general anesthesia.

Masimo company will provide 50 sensors because we need to include potential drop-offs (20%). After obtaining approval from Research Ethics Committee, we will receive the Equipment Loan Agreement from Masimo Company.

Appendices

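### Must the plan commit to reporting how often the nasal sensor gives no reading before the position can be called validated?

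*Combined protocol and SAP*

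**What the plan says.** All references are to the combined protocol and SAP.

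- **Research Questions and Hypotheses** gives the purpose: "To determine whether this position generates similar data and validate this new alternate position". The hypothesis that follows is narrower: the lower montage clears the operative field and its values still correspond to the standard ones.
- **Population** sets 40 patients, raised to 50: "Considering a drop-out of 20" per cent. Drop-out is not defined. Sponsorship repeats the 20% as the reason for supplying 50 sensors.
- **Duration of evaluation**: "Study participants will be evaluated only during surgery".
- **Intervention** makes each patient their own control: "performing neuromonitoring using both the standard (FRONTAL) and the alternative (NASAL) montage on each patient".
- **Evaluation** lists PSi, both spectral edge frequencies, suppression ratio, EMG and artifact as compared values, "and EEG waveforms, from nasal and frontal sensors".
- **Statistical Analysis** expects, for each mode, "1800 data points per subject (1 reading every 2 seconds for 1 hour) per hour will be collected".
- **Analysis plan**: "Data from the 2 placements will be compared and analyzed using a Bland-Altman analysis and a matched-pair analysis". The only other summary named is of patient characteristics.

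No section says how an absent reading is logged or counted, or how a patient whose nasal sensor never reads is classified. Appendix A, the collection form, is listed but not reproduced.

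**The concern.** Bland-Altman limits and matched-pair comparisons are computed on pairs. If the nasal sensor shows nothing for a stretch of time, or for a whole patient, those moments form no pair and leave no mark on the result. A position that nearly always reads and one that often fails could then report the same limits of agreement.

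The drop-out allowance sharpens the worry. Patients are observed only in the operating room, so there is no later follow-up to lose, and it is natural to ask what a 20% loss consists of. If nasal failures were absorbed into it, as many as 10 patients could leave the comparison while the target of 40 was still met. For an anaesthetist choosing a site because the forehead is unavailable, the chance of getting a value at all matters as well as its closeness to the frontal one. A claim of validation resting on agreement alone would be silent on that.

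**Working it through.** **1. The plan's own figures.** Inputs: 40 evaluable patients and 20% drop-out (Population); one reading every 2 seconds (Statistical Analysis).

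- Recruitment: 40 / (1 − 0.20) = 50, as stated. The allowance is 50 − 40 = 10 patients.
- Readings: 3600 s / 2 s = 1800 per hour, as stated.

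Both figures reproduce exactly.

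**2. What could go unseen by patient.** Suppose 40 are analysed, k of the 10 losses are nasal failures, and the rest are lost before placement. Attempts = 40 + k and success = 40 / (40 + k), with Clopper-Pearson intervals. The values of k are assumptions; the documents give none.

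| k | Success | Exact 95% CI |
|---|---|---|
| 0 | 40/40 = 100% | 91.2 to 100% |
| 5 | 40/45 = 88.9% | 75.9 to 96.3% |
| 10 | 40/50 = 80.0% | 66.3 to 90.0% |

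The limits of agreement are the same in all three rows, but only because the same 40 patients are used by construction. The table shows what limits of agreement do not measure. It is no evidence that such failures will occur.

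**3. What could go unseen within a patient.** Assume the frontal record is complete and 1%, 5% or 10% of nasal readings are absent.

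- 0.01 × 1800 = 18 readings, 36 s or 0.6 min per hour
- 0.05 × 1800 = 90 readings, 180 s or 3 min per hour
- 0.10 × 1800 = 180 readings, 360 s or 6 min per hour

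**4. Whether these losses would in fact be invisible.** That depends on how the device logs a lost signal, which the documents do not state. If it is logged as missing, the pair disappears. If it is logged as zero, as a held value or with high artifact, the loss enters the pairs and alters the planned comparison. The Acronyms section defines artifact as detected noise on a 0 to 100% scale. Comparing it between sensors informs on signal quality, but it is not a count of absent readings.

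**5. Whether the text sends nasal failures into the drop-out.** It does not. Duration of evaluation rules out loss to later follow-up, but the recruitment section provides another route: patients are identified at a preoperative visit and their eligibility is confirmed again at the pre-surgical visit, so some can be lost before any sensor is placed. The 50 sensors under Sponsorship match the 50 recruits and do not settle the cause of loss.

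**6. Effect on the planned sample.** An availability summary would leave 40 and 50 unchanged. With 50 attempts it would carry, for example, a no-reading rate of 0/50 = 0% (exact 95% CI 0 to 7.1%) or 5/50 = 10% (3.3 to 21.8%). These counts are again assumptions.

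**The case for a change.** The strongest case for a change is that the stated purpose goes beyond the hypothesis. Validating a position includes showing that it yields a reading, particularly where usual placement is difficult. A field on an unseen form is not a commitment to report it, and a definition of an absent reading fixed in advance cannot be chosen to suit the results. The request needs no extra patients or procedures.

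Part of this stands. No section commits to the count, artifact and EMG do not replace it, and a reader of the results would want it beside the limits of agreement.

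The rest does not carry the point from omission to error. The harm requires that lost signal be logged as missing, that nasal failures be numerous, and that analysts label them drop-outs without saying so. The documents support none of the three. It is also tempting to multiply the 95% content of the limits by availability, for example 0.95 × 40/50 = 76.0%, and call that coverage. This treats a missing reading as one outside the limits, which mixes availability with agreement and puts a precise figure on an assumed rate. Nor is the work only one extra table: a usable definition depends on device logging that is not yet described.

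**Conclusion.** No change to the plan follows. This is missing reporting detail that analysts fill sensibly. A report of a paired device comparison would ordinarily state how many patients were attempted and analysed, why others were lost, and how many readings from each sensor were usable. Nothing in the plan prevents this or points the other way.

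The planned limits of agreement remain a correct answer to the hypothesis that the two positions give corresponding values, and the primary end-point already brings signal quality in through artifact, EMG and waveforms. Recruitment of 50 is correct.

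The size of any effect is unknown. The bound within the drop-out allowance is 10 nasal failures among 50 attempts, a success rate of 80.0% (exact 95% CI 66.3 to 90.0%); with no nasal failures it is 40/40 (91.2 to 100%). The bound assumes that every loss is a nasal failure, which the documents do not say.

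The conclusion rests on two readings of the text: that no rule excludes or relabels nasal failures, and that the hypothesis under test is agreement. If a report claimed validation without giving the numbers attempted and analysed, the criticism would belong to that report.

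### The only stated hypothesis makes similarity (95% shared variance) the null, and a study meant to validate the nasal position sets no agreement limit in advance

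*Combined protocol and SAP*

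**What the plan says.** Research Questions and Hypotheses gives the purpose: "To determine whether this position generates similar data and validate this new alternate position". The hypothesis is that the nasal montage "would still have corresponding values", with no number attached.

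The primary end-point (Evaluation) is worded as a comparison, "We will monitor and compare processed electroencephalograph (EEG) values", covering six processed values and the EEG waveforms, without a threshold.

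Statistical Analysis opens with the sampling rate, "1800 data points per subject (1 reading every 2 seconds for 1 hour) per hour will be collected", and the condition "Assuming a maximum interclass correlation coefficient of .90". It then says that 40 patients are needed to "test the null hypotheses that the two modes of measurement share 95% of their variance", and that this is done "via the construction of a 95% confidence interval that ranges no more than +-5"%. No formula is named.

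The Analysis plan gives the comparison in one sentence: "Data from the 2 placements will be compared and analyzed using a Bland-Altman analysis and a matched-pair analysis". It sets no limit for the Bland-Altman results and no decision rule for the matched-pair analysis.

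**The concern.** A study that wants to show similarity needs a null of dissimilarity, so that the data must supply the evidence. Here the single formal hypothesis starts from similarity. If that sentence were followed as a test, a nasal position with less shared variance than intended could be kept as similar simply because 40 patients did not contradict it.

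Shared variance is also a measure of association. If every nasal reading were higher than its frontal partner by the same amount, shared variance would not change.

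Bland-Altman analysis does measure agreement and does not depend on the direction of the null. But it only reports bias and limits of agreement; whether these are acceptable needs a limit fixed beforehand. Without one, the word validated has no basis set in advance.

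**Working it through.** **Inputs from the plan:** 40 patients; shared variance R² = 0.95; 95% confidence interval within ±5%; coefficient 0.90; 1800 readings per patient per placement. **Assumed:** Fisher z on r = √R², SE = 1/√(n − 3), two-sided 5%, because the plan names no method.

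**1. The plan's own figure.** At R² = 0.95, r = 0.9747 and atanh(r) = 2.1783. With n = 40, SE = 1/√37 = 0.1644 and 1.96 × SE = 0.3222. The limits 1.8561 and 2.5005 transform back to R² of 0.907 and 0.973, that is −4.3 and +2.3 points (half-width 3.3). So 40 meets ±5% at an observed 95%.

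The number 40 itself is not reproduced. The smallest n is 22 (half-width) or 33 (lower arm). With a design effect of 1 + 1799 × 0.90 = 1620.1 it is 20 or 30 patients. The drop-out step does reproduce: 40/(1 − 0.20) = 50.

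The realised interval meets ±5% only if the observed value is at least 92.3% (half-width) or 94.2% (lower arm). If the truth is 95%, the probabilities are 0.91 and 0.69.

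**2. The bare test when the true shared variance is 90%.** atanh(√0.90) = 1.8184, so d = (1.8184 − 2.1783)/0.1644 = −2.189. P(not rejected) = Φ(1.96 + 2.189) − Φ(−1.96 + 2.189) = 1.000 − 0.590 = 0.41.

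- Other true values at n = 40: 0.061 at 85% and 0.685 at 92%.
- If 0.90 is the correlation of readings within a patient, the effective n is 72,000/1620.1 = 44.4, or 72,000/(1 + 1799 × 0.81) = 49.4 when the design effect is taken for a correlation. P(not rejected) at a true 90% is then 0.36 or 0.31.

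**3. The test with the ±5% clause also applied to the realised interval.** At n = 40 the null is retained for observed values from 90.7% to 97.3%. Adding the clause raises the lower end to 92.3% or 94.2%. At a true 90%, the probability falls to 0.199 (half-width) or 0.0447 (lower arm).

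A simulation of 40,000 trials with independent bivariate-normal pairs gave 0.434 for the bare test, and 0.215 and 0.051 with the clause, close to the formula.

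An interval can satisfy the clause and settle little: an observed 92.3% has an interval of 85.9% to 95.9%, half-width 5.0 points, which still contains 95%.

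**4. Constant offset.** Assume SD 10 in each placement and R² = 0.95. The SD of the differences is √(2 × 100 × (1 − 0.9747)) = 2.25, so the limits of agreement are the offset ± 1.96 × 2.25 = ± 4.4. With an offset of 15 points they are 10.6 to 19.4. The correlation is unchanged, so the shared-variance null is still retained 95% of the time. Bland-Altman shows the offset; the stated hypothesis does not.

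**5. Search for a limit.** The research questions, the primary end-point, the sample-size paragraph, the Analysis plan and the parameter definitions give no acceptable bias, limits of agreement, equivalence margin or minimum correlation for success.

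**The case against.** The best defence is that the null appears only in the sample-size sentence, which can be read as a clumsy precision target. On that reading 40 patients suffice at an observed 95%, and the planned comparison is Bland-Altman, which the direction of the null does not touch. The Analysis plan names no shared-variance test. Clearly low shared variance would mostly be caught: a true 85% escapes only about 6% of the time.

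All of this stands. It reduces the null to a wording error on the precision reading, and it means the pass rates depend on how the sentence is read. It does not supply the missing agreement limit, which is absent on every reading.

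A reader might go further and infer that the study will declare the nasal position validated by failing to reject, with a 41% false-pass rate. The documents do not say this: no section treats non-rejection, or a non-significant paired difference, as validation. A reader might also infer that a smaller study would pass more easily. That holds for the bare test (68% at n = 20 against 41% at n = 40, true 90%) but reverses if the ±5% clause must be met (6% or 1% at n = 20 against 20% or 4%).

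**Conclusion.** The concern holds, and it should be fixed. The aim is to show similarity, the only formal hypothesis assumes it, and no agreement limit is stated in advance. The missing limit is the weightier half. The reversed null matters in practice only if the sentence is carried out as a test.

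The size is conditional. At a true shared variance of 90%, the chance of keeping the 95% null runs from about 4% to 41%, depending on whether ±5% is a condition, how it is measured, and what effective n the 0.90 coefficient implies. These figures assume Fisher z and independent pairs. They illustrate the weakness and are not an error rate that the plan commits to.

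The failure to reproduce 40 does not show that 40 is too few: it meets the stated precision at an observed 95%, and the sponsor's formula is not given.

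**What to change.** (a) Delete the hypothesis-test clause and restate the sentence as precision, using the sponsor's own method and saying how the 0.90 coefficient enters. If Fisher z is that method: *At an observed shared variance of 95%, 40 patients give a 95% confidence interval of about 91% to 97%.* Draw no pass or fail from it.

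(b) Base any validation claim on agreement, with dissimilarity as the null. Add to the Analysis plan: *For each numeric parameter on which validation will be claimed, an agreement limit is stated before the data are analysed. Similarity is claimed only if the confidence interval of the chosen Bland-Altman quantity (bias, limits of agreement, or both), allowing for repeated readings per patient, lies within that limit.* The sponsor chooses the form and the value; the documents give none and none is proposed here. Waveforms, and any parameter without a limit, are reported descriptively with no validation claim.

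(c) Report the matched-pair analysis as the mean nasal-minus-frontal difference with its 95% confidence interval.

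**Cost.** One sentence is reworded, a short rule is added, and a limit must be agreed for each parameter to be validated. No extra patients are requested.

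The downside is that a limit can be missed. Under one strict form of the rule (outer 95% confidence limits of both limits of agreement inside the margin), 40 patients meet it 35% of the time at a margin of 2.5 SDs of the differences, 80% at about 2.9 and 90% at about 3.0. These are simulated figures for a single parameter, with one normal difference per patient and no true bias. Normality is doubtful for the values bounded at 0 and 100%. If a limit is missed, the claim stays descriptive.

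### Forty patients are justified by the precision of shared variance, which cannot show agreement, and the planned Bland-Altman analysis is not linked to that target or to the repeated readings within patients

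*Combined protocol and SAP*

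**What the plan says.** All references are to the combined protocol and SAP.

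- **Aim** (Research Questions and Hypotheses): "To determine whether this position generates similar data and validate this new alternate position". The hypothesis is that the lower montage "would still have corresponding values".
- **Data** (STATISTICAL ANALYSIS): for each placement, "1800 data points per subject (1 reading every 2 seconds for 1 hour) per hour will be collected". Duration of evaluation describes "time alignment in both Masimo Roots" and observation "from the moment of induction to anesthesia up to a few minutes after the extubation".
- **Size** (STATISTICAL ANALYSIS): "Assuming a maximum interclass correlation coefficient of .90, a sample size of 40 patients will be required" to test that "the two modes of measurement share 95% of their variance via the construction of a 95% confidence interval that ranges no more than +-5" per cent. No other reason for 40 is given. Recruitment of 50 allows for 20% drop-out.
- **Analysis** (Analysis plan): after descriptive statistics, "Data from the 2 placements will be compared and analyzed using a Bland-Altman analysis and a matched-pair analysis".

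The plan gives no expected SD of the differences between placements, no precision for the bias or the limits of agreement, no single primary parameter among those listed under Evaluation, and no account of how repeated readings within a patient enter the analysis. It does not define the matched-pair analysis or say what the .90 refers to.

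**The concern.** The aim is a claim about agreement: does the nasal sensor give the values that the frontal sensor gives? Shared variance (R-squared) answers a different question, namely how closely the two sets of readings follow a straight line. A constant offset leaves it unchanged. It also rises when readings span a wider range, and recording from induction to after extubation is likely to give a wide one. The ±5% therefore says nothing about how precisely the bias and the limits of agreement will be known, and these are what a Bland-Altman analysis reports.

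The second part concerns the unit of analysis. Readings two seconds apart in one patient are not independent. A Bland-Altman analysis with no further specification leaves open whether the readings are pooled or the patients are treated as the units. The choice changes the width of the reported intervals by an order of magnitude or more.

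**Working it through.** **1. The plan's own figure.** Inputs from STATISTICAL ANALYSIS: R-squared 0.95, n = 40, 95% CI. Take one independent value per patient and the Fisher z interval.

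- r = √0.95 = 0.9747; z = atanh(r) = 2.178
- half-width on the z scale = 1.96/√(40 − 3) = 0.322
- r from 0.9523 to 0.9866, so R-squared from 0.907 to 0.973

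The arms are −4.3 and +2.3 points, within ±5. On this reading the smallest n whose lower arm is within 5 points is 33, so 40 meets the bound without being the minimum. The plan names no formula, and none of the variants tried returned 40 as the minimum. The allowance for drop-out reproduces: 40/(1 − 0.20) = 50.

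**2. What shared variance misses.** Illustration with assumed values: frontal SD 12 points, nasal = frontal + 10 + independent noise.

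- Noise SD that gives R-squared 0.95: 12 × √(0.05/0.95) = 2.75
- Bias 10; limits of agreement 10 ± 1.96 × 2.75 = 4.6 to 15.4
- R-squared is 0.95 with or without the 10-point offset
- Same noise (variance 7.58), different range: frontal SD 4 gives 16/(16 + 7.58) = 0.68; frontal SD 20 gives 400/(400 + 7.58) = 0.98

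The disagreement between placements is identical in the last two cases, yet R-squared goes from 0.68 to 0.98.

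**3. Precision if all readings were treated as independent.** N = 40 × 1800 = 72,000 pairs (one hour). Half-widths are in units of the SD of single-reading differences.

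- Bias: 1.96/√72,000 = 0.0073
- Each limit: 1.96 × √(1/72,000 + 1.96²/(2 × 71,999)) = 0.0125

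**4. Precision with patients as the units.** Set the total variance of differences to 1, with p the between-patient share and 1 − p the within-patient share. Let m be the number of effectively independent readings per patient, and t(39 df) = 2.023. The documents give neither p nor m, so both are assumed. Differences are taken as approximately normal.

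- A = p + (1 − p)/m
- Bias half-width = t × √(A/40)
- Var(total variance) = 2A²/39 + (1 − 1/m)² × 2(1 − p)²/(40(m − 1))
- Limit half-width = t × √(A/40 + 1.96² × Var(total variance)/4)

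Example, p = 0.1 and m = 5: A = 0.1 + 0.9/5 = 0.28. Bias: 2.023 × √(0.28/40) = 0.169. Var(total variance) = 0.00402 + 0.00648 = 0.01050. Limit: 2.023 × √(0.00700 + 0.9604 × 0.01050) = 0.264.

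| Share p | m = 5: bias, limit | m = 20: bias, limit | m = 1800: bias, limit |
|---|---|---|---|
| 0.1 | 0.169, 0.264 | 0.122, 0.163 | 0.101, 0.111 |
| 0.3 | 0.212, 0.315 | 0.185, 0.248 | 0.175, 0.221 |
| 0.5 | 0.248, 0.377 | 0.232, 0.334 | 0.226, 0.319 |
| 0.7 | 0.279, 0.444 | 0.270, 0.421 | 0.268, 0.413 |
| 0.9 | 0.307, 0.515 | 0.304, 0.508 | 0.303, 0.505 |

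Across the grid the bias half-width is 0.101 to 0.307 SD and the limit half-width 0.111 to 0.515 SD. Against step 3 these are about 14 to 42 times wider for the bias (0.101/0.0073 to 0.307/0.0073) and 9 to 41 times wider for the limits (0.111/0.0125 to 0.515/0.0125).

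**5. One mean difference per patient.** If the data were reduced this way, the half-widths would be 2.023/√40 = 0.32 for the bias and 2.023 × √(1/40 + 1.96²/78) = 0.55 for each limit, in units of the SD of those means. Such limits do not describe single readings: their width is √A of the single-reading limits, for example √0.145 = 0.38 at p = 0.1 and m = 20.

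**The case against.** The best defence has four parts.

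- **The shared-variance test is part of the plan.** It is stated as a hypothesis with a confidence interval under STATISTICAL ANALYSIS, and the Analysis plan follows under the same heading. The undefined matched-pair analysis might even be that test. This stands: a reader might infer that the sized quantity will never be analysed, but the documents show only that the two are not linked. Adding the shared-variance interval to the Analysis plan would make the text consistent, yet the precision of the bias and limits would still be unstated.
- **Forty meets the stated bound.** This also stands. A reader might infer that the trial is too small or that its arithmetic is wrong. Step 1 does not support that. Because no SD, target precision or acceptable limits are stated, no required number can be computed for agreement either.
- **Nothing says that readings will be pooled.** Correct. A reader might infer that 72,000 readings will be analysed as independent. The documents are silent on this, and the 0.007 SD shows what the silence permits, not what is planned.
- **The planned Bland-Altman analysis would itself show an offset, and its intervals can be computed afterwards.** True, and this limits the harm. Intervals computed afterwards are valid only if the unit of analysis is right, which is the part left open.

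A fair caution also applies to the table. The SD multiples depend on assumed p and m, have no target to be compared with, and rest on normality. PSi is bounded at 0 to 100, and SR, ARTF and EMG at 0 to 100%, so normality may fail for some parameters. At low p the number of effective readings matters: at p = 0.1, going from m = 20 to m = 5 widens the limit half-width from 0.16 to 0.26 SD. The table is an illustration and should not be pasted in as a justification.

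**Conclusion.** The point holds as a mismatch between the aim, the quantity used for sizing and the stated analysis. Shared variance cannot establish that the nasal placement gives similar values. The Bland-Altman analysis that could do so is not specified for repeated readings and has no stated precision.

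Its size: with patients as the units, 40 patients give 95% CI half-widths of about 0.10 to 0.31 SD for the bias and 0.11 to 0.51 SD for each limit, against about 0.007 and 0.012 SD if readings were treated as independent. The first pair of ranges rests on between-patient shares of 0.1 to 0.9, 5 to 1800 effective readings per patient and approximately normal differences, none of which the documents supply. The second takes one hour of readings in each of 40 patients.

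The number of patients is not shown to be wrong, and enrolment and data collection are unaffected. The change should be made because it is nearly free and governs how firmly the study can claim validation. The undefined matched-pair analysis and the unexplained .90 are secondary.

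**What to change.** Keep 40 evaluable patients and make these changes under STATISTICAL ANALYSIS.

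1. **Analysis.** Suggested wording:

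> Agreement will be judged by a repeated-measures Bland-Altman analysis of the time-aligned nasal and frontal readings. Patients are the independent units. Between-patient and within-patient variance components are estimated separately, and 95% confidence intervals are reported for the bias and for each limit of agreement. Shared variance is reported as a supporting measure and is not a criterion for validation.

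2. **Sample size.** Replace the ±5% statement with the expected precision of the bias and limits for one named primary parameter, using an SD of differences supplied by the authors. Label any figures in SD multiples as illustrations, and state the assumed variance share, the assumed effective readings and approximate normality beside them.

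3. **Per-patient means.** If one mean difference per patient is also analysed, say that its limits do not apply to single readings.

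4. **Clarification (secondary).** Define the matched-pair analysis and say what the .90 refers to.

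Cost: one paragraph and one sentence are reworded, with no added patients, sensors or data. The simple ±5% statement is lost, and the reported intervals will be wider than a pooled analysis would give. Until the authors supply an SD, the new precision cannot be expressed in PSi points or compared with ±5%.
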